# 4.3.3 Investigational Medicinal Product Accountability

All IMPs required for completion of this study will be provided by the Sponsor. The study site will acknowledge receipt of the IMP supplied by the Sponsor per agreed method (e.g., returning the appropriate documentation form or updating IWRS) by the study team. Any damaged shipments will be replaced.

IMPs will either be disposed of at the study site according to the study site's institutional standard operating procedure or be returned to the Sponsor (if supplied by the Sponsor) with the appropriate documentation. The site's method of destroying Sponsor-supplied IMPs must be agreed to by the Sponsor. The site must obtain written authorization from the Sponsor (or Sponsor representative) before any Sponsor-supplied IMP is destroyed, and IMP destruction must be documented on the appropriate form.

Accurate records of all IMPs received at, dispensed from, returned to, and disposed of by the study site should be recorded on the Drug Inventory Log.

## 4.3.4 Continued Access to FHTR2163

Patients may be eligible to receive FHTR2163 as part of an open-label extension study offered by the Sponsor (Genentech, a member of the Roche Group), as described in Section 3.1.1. The Roche Global Policy on Continued Access to Investigational Medicinal Product is available at the following website:

http://www.roche.com/policy continued access to investigational medicines.pdf

#### 4.4 CONCOMITANT THERAPY

Concomitant therapy consists of any medication (e.g., prescription drugs, over-the-counter preparations) other than protocol-specified procedural medications (e.g., dilating drops) and pre- and post-injection medications (e.g., proparacaine) used by a patient in addition to protocol-mandated treatment from 7 days prior to initiation of study drug (Day 1) to the study completion/discontinuation visit. All such medications should be reported to the investigator and recorded on the Concomitant Medications eCRF.

# 4.4.1 Permitted Therapy

In general, investigators may manage patients' preexisting conditions or new-onset conditions as clinically indicated and per local standard practice, with the exception of prohibited therapies defined in Section 4.4.2. Patients who use other maintenance therapies should continue their use. Of note, the following are some common therapies that are permitted:

- Onset of ocular hypertension or glaucoma in the study eye during study participation should be treated as clinically indicated
- Onset of cataract or posterior capsular opacification in either eye during study participation may be treated as clinically indicated

Dose-interruption criteria (see Section 5.1.5 and Table 1) may apply with cataract surgery.

- Corticosteroids (ITV, subtenon, topical, device implant, oral, or IV)
- Patients who use hormone-replacement therapy or other maintenance therapy should continue their use
- Anti-VEGF treatment in the non-study eye is permitted

Intravitreal administration of FDA-approved anti-VEGF agents is permitted at the discretion of the evaluating investigator if a patient's non-study eye requires treatment for neovascular AMD (nAMD). Treatment in the non-study eye may be administered at the same visit as the study eye treatment; however, all study assessments and study eye treatment per protocol should be completed prior to anti-VEGF administration in the non-study eye. Individual trays and sterile preparation must be separately prepared for each eye treatment.

 Paracentesis in the study eye after study drug administration is permitted per clinical judgment for treatment of adverse events

For patients with a history of repeated paracentesis after study drug administration, refer to treatment interruption criteria (see Table 1).

## 4.4.2 Prohibited Therapy

At the discretion of the investigator, patients may continue to receive medications and standard treatments administered for other conditions. However, the following medications/treatments are prohibited during the study, and patients who receive any of the following therapies may have study treatment interrupted or discontinued and/or may be discontinued from the study (see Section 5.1.5):

- Systemic anti-VEGF agents
- ITV anti-VEGF agents in the study eye
- Concurrent non-study eye treatment with unapproved anti-VEGF therapy for nAMD
- Systemic or intravenous immunomodulatory therapy (e.g., azathioprine, methotrexate, mycophenolate mofetil, cyclosporine, cyclophosphamide, anti-tumor necrosis factor agents, eculizumab, tocilizumab)

- Treatment with photodynamic therapy in either eye
- Other experimental therapies including, but not limited to, stem cell treatments, gene therapy, and long-acting delivery platforms/formulations
- Prophylactic paracentesis in the study eye prior to study treatment administration (not including anterior chamber paracentesis to enable collection of aqueous humor samples)

For patients that require prophylactic paracentesis prior to study drug administration, refer to treatment interruption criteria (see Table 1).

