Randomization will be stratified by HtrA1 risk-variant carrier status (HtrA1 risk-variant carrier vs. HtrA1 risk-variant non-carrier), baseline GA lesion size (<9.0 mm² vs. ≥9.0 mm²), and annualized prebaseline GA progression rate (<1.9 mm²/yr vs. ≥1.9 mm²/yr). HtrA1 risk-variant carriers and HtrA1 risk-variant non-carriers may be enrolled in either FHTR2163 or sham-control arms.

After randomization on Day 1, patients will be administered the first ITV injection of FHTR2163 or sham control by the investigator. If a site has an unexpected issue (e.g., unable to assign the study kit), with the Medical Monitor's permission, the patient's first study treatment may be administered within 3 working days of the Day 1 visit. The following assessments will be repeated on the day of the study treatment: slit lamp examination, indirect ophthalmoscopy, and pre- and post-treatment intraocular pressure (IOP) measurement (and recorded on the Day 1 electronic Case Report Form [eCRF]).

Subsequent study treatment visits will be scheduled Q4W or Q8W relative to the Day 1 visit date. Study treatment should not occur earlier than 22 days after the previous treatment. Missed study treatments will not be made up.

At the subsequent visits, patients will have safety evaluations performed by the investigator prior to receiving study drug or sham control. Patient self-administered anti-microbials pre- and post-injection may be used at the investigator's discretion. Patients will be educated as to signs and symptoms of post-injection adverse events and instructed to contact the investigator at any time if they have any health-related concerns. All assessments for a scheduled visit will be performed on the same day, (with the exception of assessments performed during the prebaseline screening period or baseline screening window, which may be performed at any time during the 90-day or 30-day time frame, respectively). After the Day 1 visit, if a patient misses a study visit when ocular images are scheduled to be taken (see Appendix 1 and Appendix 2), the images must be obtained at the next scheduled visit.

Patients who are prematurely discontinued from study treatment (but have not withdrawn consent) will be encouraged to undergo as many scheduled visits as possible with emphasis on completing Week 72 visit.

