## 4.2.2 Masking

This is a single-masked study with patients masked to their treatment assignment (study drug vs. sham control). The BCVA examiner will also be masked to the study eye and treatment assigned. The BCVA examiner will only be permitted to perform the refraction, BCVA assessment, and pretreatment IOP measurement. The BCVA examiner will also be masked to the BCVA scores from the patient's previous visits and may only have access to a patient's refraction data from previous visits. Other site study staff will not be masked to the patient treatment assignments.

The central reading center review team, consisting of graders and ophthalmologists experienced in the conduct of clinical trials, will be masked to patients' treatment assignment. They will conduct masked independent review of CFP, FAF, NI, SD-OCT, and OCT-A images to provide an objective assessment of image evaluations.

Contract research organization (CRO) personnel, including clinical research associates, will not be masked to the patient treatment assignments.

Sponsor personnel (except for IMC members) will be masked to treatment assignment until after database lock, unless there is a need to unmask as determined by the IMC. Furthermore, personnel responsible for PK/PD sample management, assays, and analysis may be unmasked as needed (i.e., to evaluate PK relationship to an adverse event). Additionally, for regulatory reporting purposes and if required by local health authorities, the Sponsor will break the treatment code for all serious, unexpected suspected adverse reactions that are considered by the investigator or Sponsor to be related to study drug.

Patients will be masked to HtrA1 risk-variant carrier status.

Patients, site study investigator and staff (study coordinators, etc.), and Sponsor personnel (except for IMC members) will be masked to prebaseline GA growth rate unless there is a need to unmask as determined by the IMC.

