# 4.6.2 Patient Discontinuation from the Study

Patients discontinued or withdrawn from study will return to the clinic for a study discontinuation visit after a minimum of 30 days following his or her final study treatment (see Appendix 1 and Appendix 2).

Patients have the right to voluntarily withdraw from the study at any time for any reason. In addition, the investigator has the right to withdraw a patient from the study at any time.

Reasons for patient discontinuation from the study may include, but are not limited to, the following:

- Patient withdrawal of consent
- Study termination or site closure
- Adverse event
- Loss to follow-up
- Patient non-compliance, defined as failure to comply with protocol requirements as determined by the investigator or Sponsor

Every effort should be made to obtain a reason for patient discontinuation from the study. The primary reason for discontinuation from the study should be documented on the appropriate eCRF. If a patient requests to be withdrawn from the study, this request must be documented in the source documents and signed by the investigator. Patients who withdraw from the study will not be replaced.

If a patient discontinued the study but has not withdrawn the informed consent, the site should make every effort to continue to follow up on serious adverse events, deaths, and adverse events of special interest in these patients.

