# 5.1.5 Dose-Interruption and/or Treatment Discontinuation Criteria

Study-treatment interruption and patient discontinuation from the study treatment for adverse events will be determined using the criteria listed in Table 1. If treatment is interrupted, treatment will not be resumed earlier than the next scheduled study visit. The reason for study treatment interruption or discontinuation should be recorded on the appropriate eCRF and, if applicable, on the Adverse Event eCRF (see Section 5.2.1 for definition of an adverse event). Adverse events should be reported to the Sponsor in accordance with instructions provided in Sections 5.2–5.6.

In addition, for any patient who develops any of the exclusion criteria (Section 4.1.2) after study onset, dosing may be interrupted or the patient may be discontinued from study treatment after discussion with the Medial Monitor.

Additionally, patients who receive any of the prohibited therapies (Section 4.4.2) may have study treatment interrupted or discontinued and/or may be discontinued from the study.

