#### 6.4.1 Primary Efficacy Endpoint

The primary efficacy endpoint is the mean change in GA area from baseline to Week 72 as measured by FAF.

Comparison of each active arm versus the pooled sham-control arm will be assessed using a linear mixed-effect model with an effect for treatment and with covariate adjustments for baseline factors such as HtrA1 risk-variant carrier status, baseline GA lesion size, and annualized prebaseline GA progression rate. The primary analysis will be based on all available data up to 72 weeks, with no imputation for missing data. Two-sided 80% confidence interval will be provided for the estimated treatment effects. Hypothesis testing will be conducted at the two-sided significance level of 20%, and no multiple-testing adjustment is planned.

Detailed specifications of the statistical methods will be described in the DAP.

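### Sections 4.4.2 and 5.1.5 allow whole-study discontinuation after a prohibited therapy, with no criterion and no instruction to obtain the Week 72 outcome

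*Combined protocol and SAP*

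**What the plan says.** **Rule on prohibited therapy.** Section 4.4.2 lists therapies that are not allowed, among them "ITV anti-VEGF agents in the study eye", and says that "patients who receive any of the following therapies may have study treatment interrupted or discontinued and/or may be discontinued from the study". Section 5.1.5 repeats that such patients "may have study treatment interrupted or discontinued and/or may be discontinued from the study". Neither names who decides or gives a criterion for choosing between the options.

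**Who can remove a patient.** Section 4.6.2 says that "the investigator has the right to withdraw a patient from the study at any time". Its reasons for leaving the study include "Patient non-compliance, defined as failure to comply with protocol requirements as determined by the investigator or Sponsor". Section 4.2.2 masks the patient, the BCVA examiner, the reading center and Sponsor personnel outside the IMC, but "Other site study staff will not be masked to the patient treatment assignments".

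**Retention.** Under Section 3.1, patients who stop study treatment without withdrawing consent are "encouraged to undergo as many scheduled visits as possible with emphasis on completing Week 72 visit". Section 4.6.1 gives similar encouragement to the same group. A patient discontinued from the study is instead asked for one early termination visit, at least 30 days after the last treatment, and is not replaced. Section 4.6.2 then limits further follow-up to serious adverse events, deaths and adverse events of special interest.

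**Analysis.** Section 6.4.1 specifies a linear mixed-effect model: "The primary analysis will be based on all available data up to 72 weeks, with no imputation for missing data". Section 6.4 promises missing-data sensitivity analyses, with details in the DAP.

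**The concern.** The protocol clearly wants outcome data from patients who stop treatment. That aim does not reach a patient who is taken off study after a prohibited therapy, for whom no Week 72 image is requested. The early termination column in Appendices 1 and 2 includes FAF and BCVA, but at whatever time the patient leaves. It has no entry for low-luminance BCVA, a secondary endpoint.

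The loss could be selective. Study-eye anti-VEGF would ordinarily follow conversion to neovascular disease, and incident neovascular AMD is a safety endpoint in Section 2.2, so the trigger may relate to disease course or treatment. The choice between staying and leaving has no criterion, and most site staff know the assignment.

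Section 5.1.5 is also uneven. A patient who develops an exclusion criterion (CNV in either eye is one, Section 4.1.2) may have dosing interrupted or study treatment stopped; study discontinuation is not mentioned. If that patient then receives study-eye anti-VEGF, the next paragraph allows removal from the study. These passages need to be reconciled.

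At stake are completeness of the primary endpoint, the missing-at-random assumption of the observed-data model, and safety follow-up of patients who convert.

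**Working it through.** **1. The plan's own sample size.** Inputs from Section 6.1: difference 0.56 mm², SD 1.82 mm², two-sided alpha 0.20, power 80%, dropout 15%.

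- Evaluable per group: n = 2 × (1.2816 + 0.8416)² × 1.82² / 0.56² = 95.2, so 96. An exact t-test search also gives 96.
- Randomised per group: 96 / 0.85 = 112.9, so 113, against the stated 114. The total is 114 × 2.5 = 285, as stated.

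The figure reproduces, and nothing below changes it.

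**2. Precision.** With the enlarged groups of 144 (Section 3.1), t-test power for Q4W versus pooled sham is:

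| Dropout | Evaluable per group | Power |
|---|---|---|
| 15% | 122.4 | 86.9% |
| 20% | 115.2 | 85.3% |
| 25% | 108.0 | 83.5% |
| 30% | 100.8 | 81.6% |

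Loss at twice the planned rate still leaves more than 80%.

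**3. Which loss would matter.** Removal that depends only on arm or on GA area already observed is compatible with missing at random, because the model contains treatment and uses all data up to Week 72. Bias requires removal to be related to the unobserved Week 72 change beyond what the observed data explain, with an effect that does not cancel between arms.

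**4. Size, under assumptions.** The documents give no rate of prohibited-therapy use, removal or outcome difference. Let p be the share removed in an arm, and g the mean Week 72 change of removed minus retained patients, taken as equal in both arms. An observed mean misses p × g, so in absolute size

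bias = (p_active − p_sham) × g.

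Assume g of 0.5 to 1 SD, that is 0.91 to 1.82 mm².

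| Removed, active vs sham | g (mm²) | Bias (mm²) | Share of 0.56 mm² |
|---|---|---|---|
| 5% vs 2% | 0.91 | 0.03 × 0.91 = 0.027 | 5% |
| 5% vs 2% | 1.82 | 0.03 × 1.82 = 0.055 | 10% |
| 10% vs 3% | 0.91 | 0.07 × 0.91 = 0.064 | 11% |
| 10% vs 3% | 1.82 | 0.07 × 1.82 = 0.127 | 23% |
| Equal shares | any | 0 | 0% |

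For scale, the standard error at 144 per group with 15% loss is 1.82 × √(2 / 122.4) = 0.233 mm², so these biases are 0.12 to 0.55 standard errors.

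**5. Limits of the illustration.** For the mixed model, g should be read as the gap between the true Week 72 change and the model's prediction from earlier visits, so FAF taken before withdrawal may shrink it. The table is not a ceiling either. With unequal gaps the bias is p_active × g_active − p_sham × g_sham. For example, 0.10 × 1.82 − 0.03 × 0 = 0.182 mm² exceeds every row. The direction is unknown because the sign of g is unknown.

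**The case against.** The rule is permissive, and it may seldom or never be used to end study participation. Sections 4.4.2 and 5.1.5 name no decision-maker, and Section 4.6.2 lets the Sponsor, whose personnel outside the IMC are masked, determine non-compliance. Early termination FAF and BCVA are scheduled, concomitant medications and the main reason for leaving are recorded, and sensitivity analyses are promised. The increase from 285 to 360 patients was made to absorb missed visits and assessments. The study calls itself hypothesis-generating and tests at 20%. The DAP was not available, and Table 1, which holds the interruption and discontinuation criteria, is missing from the text as read; either may narrow the gap.

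Much of this stands. A reader might infer that Week 72 data will be lost informatively, that unmasked sites will make these removals, or that missing at random is broken. The documents show only that each is possible. Nor do Sections 3.1 and 4.6.1 contradict Sections 4.4.2 and 5.1.5: the former cover patients who stop treatment, the latter a wider set of options.

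The objection does not remove the gap. A discretionary rule without a criterion still permits avoidable loss, and no sensitivity analysis can recover an image that was never taken.

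**Conclusion.** The point holds as a gap in the retention rules. The protocol permits whole-study discontinuation after a prohibited therapy, gives no criterion for it, and does not extend the Week 72 instruction to the patients concerned. The resulting loss of GA area and visual acuity is avoidable and possibly informative.

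Its size cannot be derived from the documents. Under the assumed shares and a common gap, the bias runs from zero to 0.13 mm² (up to 23% of the target). It could be larger with unequal gaps, smaller once earlier FAF is used, and could go in either direction. A reader might also infer that the 15% dropout allowance, and hence power, is under threat; at 144 per group the calculation does not support that.

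This is a cheap improvement, not a flaw that undermines the primary comparison.

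**What to change.** - **Sections 4.4.2 and 5.1.5:** delete the option of study discontinuation that closes the rule, and add: *Use of a prohibited therapy does not by itself end study participation. Unless consent is withdrawn or the investigator considers further visits unsafe, the patient is encouraged to attend the remaining efficacy and safety assessments, above all FAF, BCVA and low-luminance BCVA at Week 72. Aqueous humor sampling need not continue.*
- **Section 4.6.2:** state that use of a prohibited therapy alone does not count as non-compliance leading to study discontinuation.
- **Section 5.1.5:** reconcile the paragraph on developing an exclusion criterion with the one on prohibited therapy as regards remaining in the study.

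Decisions on study treatment are left as written. Whether data after a prohibited therapy enter the primary or a sensitivity analysis is an estimand choice for the DAP; collecting them keeps both options open.

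The cost is a protocol amendment with IRB/EC approval (Section 9.6) and some further visits, already on the schedule, for a few off-treatment patients. Sample size and alpha do not change. The investigator's general right to withdraw a patient remains, so the change narrows this route to missing data without closing every other.

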#### 4.5 STUDY ASSESSMENTS

Schedules of activities to be performed during the study are provided in Appendix 1 and Appendix 2. All activities should be performed and documented for each patient.

See Appendix 1 and Appendix 2 for the schedules of activities performed for Q4W and Q8W arms, respectively.

# 4.5.1 Informed Consent Forms and Screening Log

Written informed consent for participation in the study must be obtained before performing any study-related procedures (including screening or re-screening evaluations). Informed Consent Forms for enrolled patients and for patients who are not subsequently enrolled will be maintained at the study site.

All screening evaluations and evaluations at Day 1 must be completed and reviewed to confirm that patients meet all eligibility criteria before enrollment. The investigator will maintain a screening log to record details of all patients screened and to confirm eligibility or record reasons for screening failure, as applicable.

## 4.5.2 Medical History and Demographic Data

Medical history, including clinically significant diseases, surgeries, chronic and ongoing conditions, (e.g., trauma, cancer, cardiovascular, and ophthalmic history), reproductive status, and smoking history, will be recorded at baseline. In addition, all medications (e.g., prescription drugs, over-the-counter drugs, vaccines, herbal or homeopathic remedies, nutritional supplements) used by the patient within 7 days prior to initiation of study treatment (Day 1 visit) will be recorded. At the time of each follow-up physical examination, an interval medical history should be obtained and any changes in medications and allergies should be recorded.

Demographic data will include age, sex, and self-reported race/ethnicity.

## 4.5.3 Physical Examinations

A targeted physical examination should include an evaluation of the head, eyes, ears, nose, throat, and cranial nerves. A patient's height and weight will be measured as well. Any abnormality identified at baseline should be recorded on the General Medical

History and Baseline Conditions eCRF. If any abnormalities are noted during the study, the patient may be referred to their primary care physician or an appropriate specialist for further evaluation.

Changes from baseline abnormalities should be recorded in patient notes. New or worsened clinically significant abnormalities should be recorded as adverse events on the Adverse Event eCRF.

